2.2 Treatment Assignment

Subjects will be randomized, in a 1:1 ratio to receive either placebo (BID) or Verdiperstat (600 mg BID). Randomization will be stratified by disease subtype of either MSA-P vs. MSA-C, diagnostic category of possible MSA vs. probable MSA, and country. Container assignments will be obtained by the Investigator (or designee) via the IWRS system.

2.3 Blinding and Unblinding

Blinding is critical to the integrity of this clinical study. However, in the event of a medical emergency or pregnancy in an individual subject, in which knowledge of the investigational product is critical to the subject's management, the blind for that patient may be broken by the treating physician.

Before breaking the blind of an individual subject's treatment, the Investigator should have determined that the information is necessary, i.e., that it will alter the subject's immediate management. In many cases, particularly when the emergency is clearly not investigational product related, the problem may be properly managed without the need for unblinding, by assuming that the subject is receiving active product.

Unblinding will be managed via the IWRS system. The clinical supply manager, PK and pharmacodynamic (PD) vendors, IWRS vendor, pharmacovigilance and DMC roles may be unblinded before data are unblinded for the primary endpoint and all subjects complete the study. Except as noted above, other members of the Biohaven research team will remain blinded. In cases of accidental unblinding, the Medical Monitor will be contacted and every attempt will be made to preserve the blind.

An independent DMC will monitor efficacy and safety throughout the treatment phase and will be unblinded to treatment groups. The tables, listings, and figures prepared for the closed reports will be completely unblinded revealing actual treatment groups. The unblinded statistical team will have access to treatment codes prior to database lock in order to prepare the closed reports and the DMC will have access to the unblinded reports on a secure file sharing platform. Further information regarding DMC blinding and unblinding is documented in a separate DMC Charter and DMC SAP.

During the OLE phase, all participants will not be blinded and will be receiving active Verdiperstat.

2.4 Protocol and Protocol Amendments

BHV3241-301 SAP Version 1.0 is based on BHV241-301 Protocol Version 7.0.

3 STUDY OBJECTIVES AND ESTIMANDS

3.1 Objectives

3.1.1 Primary Objectives

- To evaluate the efficacy of Verdiperstat, compared to placebo, as measured by a change from baseline in a modified Unified MSA Rating Scale (UMSARS), consisting of a subset of items from Part I and Part II, at Week 48 (see Section 6.3.2.1 for derivation of modified UMSARS).
- To assess the safety and tolerability of Verdiperstat, relative to placebo, in subjects with MSA.

[figure not shown]
3.1.2 Secondary Objectives

3.1.2.1 Key Secondary Objectives

- To evaluate the efficacy of Verdiperstat, compared to placebo, as measured by the Clinical Global Impression of Improvement (CGI-I) score at Week 48.
- To evaluate the impact of Verdiperstat on quality of life, compared to placebo, as measured by a change from baseline in the motor subscale of the MSA-Quality of Life (MSA-QoL) scale at Week 48.
- To evaluate the impact of Verdiperstat on quality of life, compared to placebo, as measured by a change from baseline in the non-motor subscale of the MSA-QoL scale at Week 48.
- To evaluate the efficacy of Verdiperstat, compared to placebo, as measured by a change from baseline in the UMSARS Part I and Part II total score at Week 48.

3.1.2.2 Other Secondary Objectives

- To assess the impact of Verdiperstat, relative to placebo, as measured by a change from baseline at Week 48 in the following instruments:
 - o Patient Global Impression of Severity (PGI-S),
 - Clinical Global Impression of Severity (CGI-S),
 - UMSARS Part III,
 - o UMSARS Part IV.

3.2 Estimands

An estimand is the target of estimation to address the scientific question of interest posed by a study objective. The 4 attributes of an estimand include the population of interest, endpoint of interest, summary of the endpoint, and specification of how intercurrent events are reflected in the scientific question of interest.

Population of Interest

The population of interest for this study is male and female patients, ≥40 to ≤80 years of age, with a diagnosis of possible or probable MSA according to consensus clinical criteria¹, including subjects with either MSA subtype, MSA-Parkinsonism (MSA-P) or MSA-Cerebellar (MSA-C). Protocol Section 5 provides a detailed description of inclusion and exclusion criteria for this study.

Endpoint

Refer to Section 4.1 for analysis sets that are used to assess endpoints.

Intercurrent Events

Intercurrent events are those that occur after treatment initiation and either preclude observation of the endpoint or affect its interpretation.

Subjects who withdrew from the study are not to be replaced.

Unless otherwise noted, efficacy analyses will be based on observed data only. For the main analyses of efficacy for primary, secondary, and endpoints, no imputation will be performed to impute data following discontinuation from study. In some cases, missing items will be imputed (see individual scales in efficacy section below). Hence all types of intercurrent events are incorporated using a treatment policy strategy, which evaluates the treatment as assigned and taken including missed or modified doses, drug discontinuation, and concurrent treatments. Study dropout including dropouts and missed visits due to COVID-19 pandemic (and corresponding discontinuation of assessments) will be handled by a hypothetical strategy to estimate what the outcome would have been at the designated time point if all subjects were continued to be assessed.

Sensitivity analyses using multiple imputation (MI) will be conducted on the primary and key secondary endpoints using a jump to reference and copy increment from reference approach to assess the impact of the missing at random (MAR) assumption (see Section 6.3.2.3).

Population-level Summary

Refer to Table 4 in Section 6.3.

Data Sources for Endpoints

UMSARS scores are from the electronic case report form (eCRF) Unified MSA Rating Scale Parts I-IV.

- CGI-I scores are from the CGI-I eCRF.
- MSA-QoL scores are from the MSA relevant Time to Event Clinical Milestones eCRF.
- PGI-S scores are from the PGI-S eCR.
- CGI-S scores are from the CGI-S eCRF.
- CCI
 CCI
 CCI
 CCI
 CCI
 CCI
 CCI
 CCI
- AEs (i.e., non-serious AEs or SAEs) are from AE eCRF.
- Central laboratory test results are from an external source.
- Local laboratory test results are from the local lab results eCRF.
- CCI
- PK concentrations and PK parameters are from an external source.

3.2.1 Primary Objective Estimand

The estimands corresponding to the primary objectives for this study are shown in Table 1.

Table 1: Primary Objective Estimands

Objective	To evaluate the efficacy of Verdiperstat, compared to placebo, as measured by a change from baseline in a modified UMSARS score at Week 48
Efficacy Endpoint	Change from baseline in a modified UMSARS score at Week 48
Summary	Using the mITT population:
	 Descriptive statistics for modified UMSARS score and change from baseline as a continuous variable by treatment group at each visit
	 Difference in mean change from baseline in modified UMSARS scores between treatment groups at week 48 estimated and tested using a mixed-effect model for repeated measures (MMRM)
Intercurrent	1) Main Analysis - Observed data only
Events	2) Supplementary Analysis 1 – While on-treatment strategy
	3) Supplementary Analysis 2 – Compliant subjects hypothetical strategy
	4) Sensitivity Analysis – Multiple imputation jump to reference and copy increment from reference
	5) Sensitivity Analysis – Observed data only using narrower visit window for Week 48
Objective	To assess the safety and tolerability of Verdiperstat, relative to placebo, in subjects with MSA
Safety Endpoint	Frequency of unique subjects with serious adverse events (SAEs), AEs leading to study drug discontinuation, AEs related to study drug, clinically significant ECG abnormalities, and clinically significant laboratory test abnormalities
Summary	Number and percentage of subjects with safety events and findings for the safety population
Intercurrent Events	Treatment policy strategy, i.e., no accounting for intercurrent event

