4.4 End of Treatment

Patients will have a Week 48/Early Discontinuation visit when they either complete the study at Week 48 or discontinue from study medication early (prior to Week 48). The Week 48/Early Discontinuation assessments/procedures should be conducted as an in person visit at the study site. Every effort should be made to conduct the Week 48 visit and maintain a +/- 7 day window. However, due to the COVID-19 public health emergency, if absolutely necessary, in order to minimize potential risks to study participant safety and to comply with governmental and local institutional guidance (e.g., study site has a policy that an in person clinical research visit must be delayed), the Week 48 visit window may be expanded beyond the +/- 7 day window up to an additional 12 weeks (maximum treatment duration of 60 weeks). However, every attempt should be made to conduct the visit as close as possible to the date that the visit is due. Under these circumstances, the Investigator should discuss the specific circumstances of these cases with the sponsor medical monitor (or designee), who must

approve the request to extend the treatment duration, prior to any modification of the visit window.

If the Week 48 visit window is modified, participants should have safety assessments evaluated remotely (e.g., via phone) and safety labs conducted (at a local lab) at the time of the scheduled Week 48 visit.

For subjects who discontinue early, depending on the reason for early discontinuation (e.g., declining patient status), some procedures (for example, PK samples, PD samples, lumbar puncture), may not be conducted at this visit. Conduct of all procedures, if possible, is encouraged. If possible, the subjects who discontinue from study medication prior to Week 48 should be contacted by a follow up phone call at the approximate time of their Week 48 visit, to collect information on clinical status (including Time to Event measures of disease progression, and if applicable, AEs, SAES).

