9.4.7 Analysis of Safety

The Investigators determine the intensity of AEs and the relationship of AEs to study therapy. The Investigators' terms are coded and grouped by system organ class using the latest version of the Medical Dictionary for Regulatory Activities (MedDRA) available. AEs will be presented by system organ class and preferred term, ordered by the overall frequency of events. If a subject had an adverse event with different intensities over time, then only the greatest intensity is reported.

AEs are tabulated in all treated subjects. All deaths and SAEs are listed for enrolled subjects without regard to onset.

The frequencies of the following safety events are summarized by treatment group and overall for treated subjects: SAEs; all AEs, non-serious AEs; AEs by intensity; AEs by relatedness and clinically relevant laboratory abnormalities.

Graphical and tabular displays of on-treatment liver function test results are provided.

Safety will be presented separately for the double-blind phase and for the open-label extension phase, overall and by randomized arm.

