6.4.1 Adverse Events

AEs will be coded using MedDRA and displayed in tables and listings by system organ class (SOC) and preferred term (PT), unless specified otherwise.

Analyses of AEs will be performed for those events that are considered treatment-emergent AEs (TEAEs), where treatment-emergent is defined as any AE that developed, worsened, or became serious on or after first dose of study drug and prior to 30 days after the last dose of study drug.

A TEAE overview without SOC and PT will be presented as the number and percentage of subjects with any of the following TEAEs: TEAE leading to death; serious TEAE; serious TEAE related to study drug; TEAE leading to study drug discontinuation; any TEAE; TEAE related to study drug; and severe AE.

In addition, TEAEs will be tabulated by SOC and PT for all treated subjects for the following endpoints for the DB and OLE phases, separately and combined:

- TEAEs
- TEAEs related to treatment (includes, possibly related and related)
- TEAEs by highest severity (mild, moderate, severe)

- TEAEs related to treatment by highest severity
- Treatment-emergent SAEs
- TEAEs leading to discontinuation of study treatment

In the above tabulations, each subject will contribute only once (i.e., the most related occurrence or the most severe occurrence) to each of the incidence rates in the descriptive analysis, regardless of the number of episodes.

The TEAEs summary by SOC and PT will also include the number of unique AE occurrences; unique occurrences mean that if a subject had an AE twice, both will be reported (i.e., the subject will contribute twice to the count of events).

All AEs occurring pre-treatment and during the entire study will be listed. Additional listings will be provided including deaths, SAEs, AEs leading to discontinuation of study drug, and events of special interest (see Section 6.4.2).

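### The primary safety estimand is labelled treatment policy, but the adverse event tables count only events up to 30 days after the last dose

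*SAP*

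**What the plan says.** **The label.** SAP Table 1 covers the objective of assessing safety and tolerability. Its endpoint is "Frequency of unique subjects with serious adverse events (SAEs), AEs leading to study drug discontinuation, AEs related to study drug", together with clinically significant ECG and laboratory abnormalities. The intercurrent-event entry is "Treatment policy strategy, i.e., no accounting for intercurrent event". SAP 3.2, describing the efficacy analyses, says that treatment policy includes drug discontinuation.

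**The counting rule.** SAP 6.4.1 confines adverse event analyses to treatment-emergent events, defined as those that begin, worsen or become serious "on or after first dose of study drug and prior to 30 days after the last dose of study drug". The overview table follows that definition, with rows that include "TEAE leading to death; serious TEAE; serious TEAE related to study drug". The tables by system organ class and preferred term use it too. SAP 6.4.3 (laboratory) and 7.1 (analysis periods) apply the same 30-day extension.

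**What happens to later events.** They go to listings. SAP 6.4.1 says "All AEs occurring pre-treatment and during the entire study will be listed", and Protocol 9.4.7 says "All deaths and SAEs are listed for enrolled subjects without regard to onset".

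**What is collected later.** Under Protocol 4.4, subjects who stop drug before Week 48 "should be contacted by a follow up phone call at the approximate time of their Week 48 visit", if possible, to obtain clinical status and, where applicable, AEs and SAEs. Protocol Table 1 and SAP Appendix I schedule AE and SAE monitoring at that call. Protocol 8.1.4 requires all SAEs only to 30 days after dosing stops. After that, only those the investigator believes related to drug or procedures are to be reported.

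**The concern.** Treatment policy for drug discontinuation means that an event counts whether or not the subject was still on drug. A window tied to the last dose does the opposite: stopping drug ends the count 30 days later. The stated rule does not deliver the stated estimand for a primary objective.

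The stakes are in the serious and fatal events. MSA is fatal, Protocol 6.4 lists disease progression among the reasons for stopping drug, and Protocol 4.4 gives declining status as an example. If the rate or timing of stopping differs between arms, the tabulated serious and fatal counts cover different lengths of follow-up in the two arms, under a label that tells the reader they do not. Narratives do not fill the gap. SAP 6.4.7 provides them for late deaths only in subjects who took at least one dose of active drug, and Protocol 4.5.1 bars early discontinuers from the extension. A late death in a placebo discontinuer would therefore be a listing line only.

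**Working it through.** **Which parts of the endpoint the cut touches**

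| Component in SAP Table 1 | Effect of the cut at last dose + 30 days |
|---|---|
| SAEs | Later onsets are not tabulated |
| AEs leading to discontinuation | Essentially none; they precede or coincide with stopping |
| Related AEs | Any late-onset related event is not tabulated |
| ECG and laboratory abnormalities | Little; neither is measured at the Week 48 call |

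Death is not a named component of the endpoint, but it is a row in the overview table. The definition attaches to the adverse event, not to the date of death. A death after day 30 from an event that began inside the window can still be counted.

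**How much follow-up lies outside the tables.** The plan gives no figure for this, so what follows is illustrative.

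Inputs from the documents:
- Treatment phase: 48 weeks, T = 336 days.
- Window after last dose: w = 30 days.
- Drop-out about 20% and 325 randomized (SAP 5.1). This figure reproduces: the effect is 0.40 × 4.88 = 1.952 with SD 4.85, which needs 130 per arm for 90% power; 260 / (1 − 0.20) = 325.

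Assumptions not in the documents: the drop-out allowance equals the drug-discontinuation rate, and stopping times are uniform over the 336 days.

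1. Mean time from stopping to Week 48: T/2 = 168 days.
2. Mean time beyond the window: (T − w)² / (2T) = 306² / 672 = 139.3 days (19.9 weeks).
3. Share of off-drug time beyond the window: 139.3 / 168 = 83%.
4. Share of planned 48-week person-time: 0.20 × 139.3 / 336 = 8.3%.
5. In person-years, both arms together: 0.20 × 325 = 65 discontinuers; 65 × 19.9 / 52 = 24.9, out of 325 × 48 / 52 = 300.

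Sensitivity of step 4:

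| Discontinuation | Timing | Days beyond window | Share of person-time |
|---|---|---|---|
| 10% | uniform | 139.3 | 4.1% |
| 20% | uniform | 139.3 | 8.3% |
| 30% | uniform | 139.3 | 12.4% |
| 20% | all stop at Day 252 | 336 − 30 − 252 = 54 | 3.2% |
| 20% | all stop at Day 84 | 336 − 30 − 84 = 222 | 13.2% |

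These are shares of calendar follow-up. Subjects who die or withdraw consent have no later follow-up to recover, so the amount that any table could regain is smaller.

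**The case against.** The best defence is that counting to last dose + 30 days is a clearly defined rule, and that the tables are openly headed treatment-emergent. No safety hypothesis is tested, so on this view only one word in Table 1 is wrong. Part of this stands. The window is stated plainly, the planned safety summary is counts and percentages, and the efficacy test is unaffected. But the label belongs to a primary objective, and Table 1 itself names a while-on-treatment strategy for an efficacy supplementary analysis, so the accurate term was available.

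A reader might infer three stronger things that the documents do not support:

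- **That nothing after drug stop is tabulated, or that late events are never compared.** The first 30 days after stopping are tabulated by arm. Protocol 9.4.7 plans SAE frequencies by treatment group with no window stated. SAP 6.4.2 and the definitions of the time-to-event measures are not in the public text, so a comparison that includes late deaths cannot be ruled out. Withdrawal reasons are tabulated (SAP 6.2.3), although they do not show what happened afterwards.
- **That discontinuers are known to be the sickest subjects, so the comparison is known to be biased.** Protocol 6.4 also lists consent withdrawal and ECG, hepatic, renal and thyroid findings as reasons to stop. Enrichment for sicker subjects is plausible, not shown.
- **That two further tables would deliver treatment policy.** Under Protocol 8.1.4, late SAEs outside the call are selected on perceived relatedness, and the call itself is made only if possible. Counting how many subjects were reached describes that selection but does not remove it.

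**Conclusion.** The point holds as a mismatch between the stated strategy and the counting rule. The tables estimate a while-on-treatment (+30 days) quantity. What is lost is mainly SAEs and fatal events that begin 30 days or more after the last dose in early discontinuers, plus any late related AEs. No by-arm table for these is visible.

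The follow-up outside the tables is about 8% of planned person-time if 20% of subjects stop drug uniformly over 48 weeks. The range is 3% to 13% across the timings examined at that rate, and 4% to 12% for rates of 10% to 30% with uniform timing. The documents give neither a discontinuation rate nor its timing, so this indicates scale only. It says nothing about the number of events or the direction of any difference between arms. The change should be made, because it concerns a primary objective and affects what the safety comparison can show.

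**What to change.** 1. In SAP Table 1, describe the TEAE summaries as while on treatment + 30 days.
2. Add two by-arm tables in treated subjects: all known deaths, and all reported SAEs. Count from first dose to Day 337 regardless of drug stop, include events learned at the Week 48 call, and cut at the first open-label dose for subjects who enter the extension.
3. Footnote, by arm, how many early discontinuers were due for the call and how many were reached.
4. State beside the SAE table that Protocol 8.1.4 requires SAEs beyond 30 days only when believed related. The later counts are therefore incomplete and should not be called a full treatment-policy estimate. Keeping that label for SAEs would need SAE collection to be aligned with the Week 48 call.

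Items 1 to 4 cost SAP wording and two tables built from whatever has been reported. The downside is incomplete late ascertainment, which the footnotes disclose but do not cure. Aligning collection would need a protocol amendment, which is a larger step. If the sponsor does not want the extra tables, item 1 alone removes the contradiction but leaves late events without a by-arm summary.

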3.2.2 Secondary Objective Estimands

The estimands corresponding to the secondary objectives are shown in Table 2.

[figure not shown]
 Table 2:
 Secondary Objective Estimands

[figure not shown]
Objective 1	To evaluate the efficacy of Verdiperstat, compared to placebo, as measured by the CGI-I score at Week 48
Efficacy Endpoint	CGI-I score at Week 48
Summary	Using the mITT population:
	 Descriptive statistics and number and percentage of subjects in each response category by treatment group at each visit Difference in mean CGI-I score between treatment groups at Week 48 estimated and tested using MMRM
Intercurrent Events	1) Main Analysis – Observed data only
	2) Sensitivity Analysis – Multiple imputation jump to reference and copy increment from reference
Objective 2	To evaluate the impact of Verdiperstat on quality of life, compared to placebo, as measured by a change from baseline in the motor subscale of the MSA-QoL scale at Week 48
Efficacy Endpoint	MSA-QoL motor subscale change from baseline at Week 48
Summary	Using the mITT population:
	 Descriptive statistics for the MSA-QoL motor subscale scores and the change from baseline in the subscale scores by treatment group at each visit Difference in mean change from baseline in the MSA-QoL motor subscales scores at Week 48 estimated and tested using MMRM
Intercurrent Events	Main Analysis – Observed data only
	 Sensitivity Analysis – Multiple imputation jump to reference and copy increment from reference
Objective 3	To evaluate the impact of Verdiperstat on quality of life, compared to placebo, as measured by a change from baseline in the non-motor subscale of the MSA-QoL scale at Week 48
Efficacy Endpoint	MSA-QoL non-motor subscale change from baseline at Week 48
Summary	Using the mITT population:
	 Descriptive statistics for the MSA-QoL non-motor subscale scores and the change from baseline in the subscale scores by treatment group at each visit Difference in mean change from baseline in the MSA-QoL non-motor subscales scores at Week 48 estimated and tested using MMRM
Intercurrent Events	1) Main Analysis – Observed data only
	2) Sensitivity Analysis – Multiple imputation jump to reference and copy increment from reference

Objective 4	To evaluate the efficacy of Verdiperstat, compared to placebo, as measured by a change from baseline in the UMSARS Part I and Part II total score at Week 48
Efficacy Endpoint	UMSARS Part I and II total score change from baseline at Week 48
Summary	Using the mITT population:
Summur y	 Descriptive statistics for the UMSARS Part I and Part II total scores and the change from baseline in the total scores by treatment group at each visit
	 Difference in mean change from baseline in the UMSARS Part I and Part II total scores at Week 48 estimated and tested using MMRM
Intercurrent Events	1) Main Analysis – Observed data only
	 Sensitivity Analysis – Multiple imputation jump to reference and copy increment from reference
Objective 5	To assess the impact of Verdiperstat, relative to placebo, as measured by a change from baseline at Week 48 in PGI-S
Efficacy Endpoint	PGI-S change from baseline at Week 48
Summary	Using the mITT population:
	 Descriptive statistics for the PGI-S score and the change from baseline score by treatment group at each visit
	 Difference in mean change from baseline in the PGI-S score at Week 48 estimated and tested using MMRM
Intercurrent Events	Observed data only
Objective 6	To assess the impact of Verdiperstat, relative to placebo, as measured by a change from baseline at Week 48 in CGI-S
Objective 6 Efficacy Endpoint	
,	from baseline at Week 48 in CGI-S
Efficacy Endpoint	from baseline at Week 48 in CGI-S CGI-S change from baseline at Week 48
Efficacy Endpoint	from baseline at Week 48 in CGI-S CGI-S change from baseline at Week 48 Using the mITT population: Descriptive statistics for the CGI-S scores and the change from baseline in the
Efficacy Endpoint	 from baseline at Week 48 in CGI-S CGI-S change from baseline at Week 48 Using the mITT population: Descriptive statistics for the CGI-S scores and the change from baseline in the scores by treatment group at each visit Difference in mean change from baseline in the CGI-S scores at Week 48
Efficacy Endpoint Summary	 from baseline at Week 48 in CGI-S CGI-S change from baseline at Week 48 Using the mITT population: Descriptive statistics for the CGI-S scores and the change from baseline in the scores by treatment group at each visit Difference in mean change from baseline in the CGI-S scores at Week 48 estimated and tested using MMRM
Efficacy Endpoint Summary Intercurrent Events	from baseline at Week 48 in CGI-S CGI-S change from baseline at Week 48 Using the mITT population: Descriptive statistics for the CGI-S scores and the change from baseline in the scores by treatment group at each visit Difference in mean change from baseline in the CGI-S scores at Week 48 estimated and tested using MMRM Observed data only To assess the impact of Verdiperstat, relative to placebo, as measured by a change
Efficacy Endpoint Summary Intercurrent Events Objective 7	 from baseline at Week 48 in CGI-S CGI-S change from baseline at Week 48 Using the mITT population: Descriptive statistics for the CGI-S scores and the change from baseline in the scores by treatment group at each visit Difference in mean change from baseline in the CGI-S scores at Week 48 estimated and tested using MMRM Observed data only To assess the impact of Verdiperstat, relative to placebo, as measured by a change from baseline at Week 48 in UMSARS Part III UMSARS Part III (orthostatic change in systolic blood pressure (BP), diastolic BP, and
Efficacy Endpoint Summary Intercurrent Events Objective 7 Efficacy Endpoint	 from baseline at Week 48 in CGI-S CGI-S change from baseline at Week 48 Using the mITT population: Descriptive statistics for the CGI-S scores and the change from baseline in the scores by treatment group at each visit Difference in mean change from baseline in the CGI-S scores at Week 48 estimated and tested using MMRM Observed data only To assess the impact of Verdiperstat, relative to placebo, as measured by a change from baseline at Week 48 in UMSARS Part III UMSARS Part III (orthostatic change in systolic blood pressure (BP), diastolic BP, and heart rate) change from baseline at Week 48
Efficacy Endpoint Summary Intercurrent Events Objective 7 Efficacy Endpoint	 from baseline at Week 48 in CGI-S CGI-S change from baseline at Week 48 Using the mITT population: Descriptive statistics for the CGI-S scores and the change from baseline in the scores by treatment group at each visit Difference in mean change from baseline in the CGI-S scores at Week 48 estimated and tested using MMRM Observed data only To assess the impact of Verdiperstat, relative to placebo, as measured by a change from baseline at Week 48 in UMSARS Part III UMSARS Part III (orthostatic change in systolic blood pressure (BP), diastolic BP, and heart rate) change from baseline at Week 48 Using the mITT population: Descriptive statistics for the UMSARS Part III results and the change from
Efficacy Endpoint Summary Intercurrent Events Objective 7 Efficacy Endpoint	 from baseline at Week 48 in CGI-S CGI-S change from baseline at Week 48 Using the mITT population: Descriptive statistics for the CGI-S scores and the change from baseline in the scores by treatment group at each visit Difference in mean change from baseline in the CGI-S scores at Week 48 estimated and tested using MMRM Observed data only To assess the impact of Verdiperstat, relative to placebo, as measured by a change from baseline at Week 48 in UMSARS Part III UMSARS Part III (orthostatic change in systolic blood pressure (BP), diastolic BP, and heart rate) change from baseline at Week 48 Using the mITT population: Descriptive statistics for the UMSARS Part III results and the change from baseline in results by parameter and treatment group at each visit Difference in mean change from baseline in the UMSARS Part III results at Week

Objective 8	To assess the impact of Verdiperstat, relative to placebo, as measured by a change from baseline at Week 48 in UMSARS Part IV
Efficacy Endpoint	UMSARS Part IV change from baseline at Week 48
Summary	Using the mITT population:
	 Descriptive statistics for the UMSARS Part IV scores and the change from baseline in scores by treatment group at each visit
	 Difference in mean change from baseline in the UMSARS Part IV scores at Week 48 estimated and tested using MMRM
Intercurrent Events	Observed data only

